3.3 Visit Descriptions

3.3.1 Visit 1

Eligible study participants will be screened, approached and consented for the study. The screening and enrollment process may be performed remotely.

3.3.2 Visit 2

3.3.2.1 The participant will then undergo EUS procedure as clinically indicated. The shear wave measurements will be obtained during EUS. Study subjects will undergo MR elastography if no results within the previous 6 months are available. Subject participation is deemed complete at the end of MRE.

3.3.3 Follow-Up Analysis

Accuracy and efficacy of EUS shear wave elastography in assessing liver fibrosis when compared to MR elastography.

3.4 Primary Safety Endpoints

There are no specific primary safety endpoints pertaining to the study as EUS shear wave and MR elastography are non-invasive investigations. There is no investigational device involved in this study.

4 Subject Selection, Enrollment and Withdrawal

All patients who are undergoing EUS procedures may be eligible for the study. Patients with an established history of chronic liver disease with associated advanced fibrosis/cirrhosis will be of particular interest to the study.

It is anticipated that we will screen up to 250 subjects and enroll 50 subjects to the study.

4.1 Inclusion Criteria

1. Adults over 18 years of age who are undergoing EUS procedures.
2. Subjects with history of chronic liver disease, advanced fibrosis, or cirrhosis.
3. Subjects without any history of chronic liver disease.
4. Subjects able to give appropriate consent to the study.

4.2 Exclusion Criteria

1. Subjects who may have MRI-*incompatible* metal implants/devices.
2. Subjects with severe claustrophobia who may not tolerate MR elastography.
3. Subjects with unreliable EUS-SWE measurements.

4.3 Subject Recruitment, Enrollment and Screening

Potential subjects will be identified by the study team referencing the procedure and surgery calendars for upcoming procedures. If patients are scheduled for an EUS, they may be contacted by study staff prior to their procedure, to gauge interest.

Potential subjects may also be identified by physician referral. These patients would also be contacted prior to their procedure to gauge interest.

Outpatient subjects may be approached about the opportunity by phone, email, portal, or in-person to discuss the study details. Inpatients may be approached by phone or in their room as allowed by the charge nurse. An electronic or paper copy of the consent may be provided via these methods, prior to consent, to discuss and address any questions.

Recruitment will take place at the pre-procedural area prior to the procedure, or study team will reach out via email or phone to convey informed consent information which may include giving a copy of the consent form for review. Consenting and enrolment of patients on day of procedure will occur in a private room on the procedural floor prior to the procedure. These rooms house only one patient at a time and closing the door and blinds will eliminate the chance of individuals outside the room from hearing or witnessing the informed consent process. 30 minutes will be provided for discussion. Minimum 30 minutes will be provided between

Revised 6/1/2021

discussion and decision allowing patients time to consider and talk with friends and/or family. Patients will have access to any glasses and/or hearing aids.

Investigators and/or study team will come to the potential subjects to explain the details of the study and obtain written informed consent and complete the questionnaires. These may also be collected digitally through Ptrax via Remote Consenting and either a video meeting or telephone meeting prior to signing the ICF. Subjects will have time ample time to learn about our study and decide if they want to enroll prior to consent.

The consent visit will occur through a video or phone consult with the subject and a witness if the subject is not able to physically sign consent. Once a time for the consent is agreed upon, the consent will be sent via email. The subject will be reminded not to sign the form prior to the consent appointment. The identity of the subject will be confirmed through the video or phone connection, as well as clinic number, name, and birthdate. A 30- minute consent appointment will be scheduled. Additional time can be added as needed. After the subjects' questions are answered and if the subject agrees, the form will be signed electronically.

Documentation of informed consent will involve the use of the Remote Electronic Consent technology. The subject may print or electronically save the form through DocuSign or from their patient portal or the subject may contact the study team to provide a copy of the form. Note: If the subject prefers not to use the Electronic Consent technology, the study team will provide a paper consent form for signature either in person or by mail.

4.4 Early Withdrawal of Subjects

4.4.1 When and how to Withdraw Subjects

The subjects will undergo EUS shear wave elastography and MRE in a sequential order, unless subjects had undergone previous MRE. If EUS shear wave measurements are unreliable (i.e., VsN < 70%). Then subjects will be withdrawn from the study and therefore will not proceed to undergo MRE, or to be included in the final analysis.

4.4.2 Data Collection and Follow-up for Withdrawn Subjects

Withdrawn subjects will be recorded in the study record in order to calculate the withdrawal rate. There will be not further utilization of any subject related data.

5 Statistical Plan

5.1 Sample Size Determination

Revised 6/1/2021

The hypothesis is at EUS-SWE is non-inferior to MRE at differentiating (“diagnosing”) cirrhosis vs those without fibrosis.

Using the pooled AUC above for MRE of 0.972, and data from our preliminary analysis that EUS-SWE had an AUC of 0.89., a sample size of 50 would give us 99% power and a sample size of 25 gives us 91% power. We anticipate screening up to 250 potential study participants.

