7 DATA HANDLING AND RECORD KEEPING.....	15
7.1 CONFIDENTIALITY.....	15
7.2 SOURCE DOCUMENTS.....	15
7.3 RECORDS RETENTION	16
8 STUDY MONITORING, AUDITING, AND INSPECTING.....	16
8.1 STUDY MONITORING PLAN	16
8.2 AUDITING AND INSPECTING	17
9 ETHICAL CONSIDERATIONS.....	17
10 STUDY FINANCES	17
10.1 FUNDING SOURCE	17
11 PUBLICATION PLAN	17

12	REFERENCES	18
13	ATTACHMENTS	ERROR! BOOKMARK NOT DEFINED.

LIST OF ABBREVIATIONS

EUS	Endoscopic Ultrasound
MRE	Magnetic Resonance Elastography
AE	Adverse Event/Adverse Experience
CFR	Code of Federal Regulations
CRF	Case Report Form
DSMB	Data and Safety Monitoring Board
FDA	Food and Drug Administration
GCP	Good Clinical Practice
HIPAA	Health Insurance Portability and Accountability Act
IRB	Institutional Review Board
PHI	Protected Health Information
PI	Principal Investigator
SAE	Serious Adverse Event/Serious Adverse Experience
SOE	Schedule of Events
SOP	Standard Operating Procedure
E	Elastic Modulus
V _s	Shear wave velocity
V _{sN}	Reliability Index
IQR/M	Interquartile Range/Median

Study Summary

Title	A Prospective Study of Endoscopic Ultrasound Shear Wave Elastography for assessment of liver fibrosis
Running Title	EUS shear wave elastography VS MRE
Title Acronym	EUS vs MRE
IRB Protocol Number	21-003779
Phase	Prospective comparative study
Methodology	Subjects who are eligible will undergo EUS for clinical indications. After completion of EUS, subjects will undergo subsequent MR Elastography if not already performed for clinical purposes. EUS Shear wave measurements will be studied to determine diagnostic accuracy when compared to MR Elastography.
Overall Study Duration	6 months Recruitment and Active study execution, 3 months analysis and 3 months publication. Total: 12 months
Subject Participation Duration	Up to 60 days screening prior to study procedure, and up to 60 days post procedure to follow-up MRE.
Objectives	To assess the diagnostic accuracy of EUS shear wave elastography in liver fibrosis staging in both normal subjects and subjects with advanced liver fibrosis/cirrhosis
Number of Subjects	Fifty (50)
Diagnosis and Main Inclusion Criteria	Subjects over 18 years of age who are scheduled to undergo endoscopic ultrasound procedure as part of clinical care.
Study Device	EUS shear wave elastography
Reference Imaging Modality	Magnetic resonance elastography (MRE)

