2.1 Primary Objective

To evaluate the diagnostic performance of EUS shear wave elastography in the assessment of liver fibrosis compared to MR elastography.

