5.2 Statistical Methods

Descriptive Statistics

Baseline values for demographic, clinical, and outcome will be tabulated for the study subjects. Continuous variables will be expressed as mean and standard deviation. Categorical variables will be expressed as percentages.

Analytical Statistics

The obtained shear wave measurements will be compared to MR elastography measurements to determine the AUC of EUS-SWE using MRE serving as the gold standard. Logistic regression will be used to generate ROC curves, and exploratory multivariable analyses using baseline differences in each group and other important clinical factors will be performed to identify confounders and interactions during the exploratory sensitivity analyses.

Handling of Missing Data

Subjects in which EUS shear wave measurements are unreliable (i.e., VsN < 70%) will not proceed to undergo MR elastography and will be excluded from the study, therefore will not be part of the statistical analysis. However, the subject will be recorded for the study to determine the rate of unreliable EUS shear wave measurements.

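### Section 5.1 hypothesises non-inferiority of EUS-SWE to MRE, but the analysis in 5.2 uses MRE as the gold standard and cannot test it; the 99%/91% power is not shown for that hypothesis.

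*Combined protocol and SAP*

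**What the plan says.** Section 5.1 (Sample Size Determination) gives the study's only hypothesis: that "EUS-SWE is non-inferior to MRE at differentiating" cirrhosis from no fibrosis. The power argument starts with "Using the pooled AUC above for MRE of 0.972", adds an AUC of 0.89 for EUS-SWE from a preliminary analysis, and concludes that "a sample size of 50 would give us 99% power and a sample size of 25 gives us 91% power". The section names no test, margin, alpha, sidedness, correlation between the methods or ratio of cases to controls. The pooled AUC is said to stand above, but the supplied text does not contain it.

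Section 5.2 (Statistical Methods) sets out the analysis: the EUS-SWE and MRE measurements are compared "to determine the AUC of EUS-SWE using MRE serving as the gold standard". No AUC for MRE, no difference of AUCs and no non-inferiority test appears there. The Study Summary agrees ("EUS Shear wave measurements will be studied to determine diagnostic accuracy when compared to MR Elastography") and lists MRE as the reference modality. The primary objective in 2.1 reads "To evaluate the diagnostic performance of EUS shear wave elastography in the assessment of liver fibrosis compared to MR elastography".

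On numbers, section 4 states: "It is anticipated that we will screen up to 250 subjects and enroll 50 subjects to the study".

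**The concern.** Non-inferiority of one diagnostic method to another is a statement about the difference between two accuracies. Both have to be scored against the same third standard. Under 5.2 MRE is that standard, so its own accuracy is fixed at 1 and no EUS-minus-MRE difference can be estimated.

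Two things are at stake. A report that followed the plan and concluded non-inferiority to MRE would have no basis for that conclusion. And the only justification for N=50 is a power figure tied to this hypothesis, with the test behind it unstated. The cited AUCs already place EUS-SWE 0.082 below MRE (0.972 − 0.89), so the power of any non-inferiority test depends heavily on a margin that is not given.

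**Working it through.** **1. What the hypothesis needs and what the analysis gives.** The hypothesis in 5.1 needs AUC(EUS-SWE) − AUC(MRE), both against one reference, and a margin. The analysis in 5.2 gives AUC(EUS-SWE) against MRE. MRE against its own classification has AUC 1 with variance 0, so the required difference is not produced.

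**2. Can 99% and 91% be recovered?** From 5.1: AUCs 0.972 and 0.89; N=50 and 25. Assumed, because not stated: equal groups unless noted, correlation r between the two AUC estimates of 0 to 0.8, and the alphas shown.

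Hanley-McNeil variance for AUC A with n₁ cases and n₀ controls:

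Var = [A(1−A) + (n₁−1)(A/(2−A) − A²) + (n₀−1)(2A²/(1+A) − A²)] / (n₁n₀)

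For A=0.89 and 25/25: (0.0979 + 24×0.0097 + 24×0.0461)/625 = 0.0023, so SE = 0.0480. In the same way:

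| Split | SE at 0.89 | SE at 0.972 | SE of difference, r = 0 / 0.5 / 0.8 |
|---|---|---|---|
| 25/25 | 0.0480 | 0.0242 | 0.0537 / 0.0415 / 0.0321 |
| 12.5/12.5 | 0.0688 | 0.0349 | 0.0771 / 0.0596 / 0.0459 |

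where SE(difference) = √(s₁² + s₂² − 2·r·s₁·s₂).

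Difference test, two-sided 0.05: power = Φ(0.082/SE − 1.96). Non-inferiority, one-sided 0.025, true difference −0.082: power = Φ((margin − 0.082)/SE − 1.96). For example, margin 0.10, r=0.5, N=50: Φ(0.018/0.0415 − 1.96) = 6%.

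| Test | N=50 | N=25 | Fits 99%/91%? |
|---|---|---|---|
| Difference, r = 0 / 0.5 / 0.8 | 33 / 51 / 73% | 18 / 28 / 43% | No |
| Non-inferiority, margin 0.10, r = 0 / 0.5 / 0.8 | 5 / 6 / 8% | 4 / 5 / 6% | No |
| Non-inferiority, margin 0.15, r = 0 / 0.5 / 0.8 | 24 / 37 / 56% | 14 / 21 / 32% | No |
| Non-inferiority, margin 0.28, r = 0.5 | 99.8% | 91.4% | Yes |
| AUC 0.89 against 0.5, about 25% cases (12/38; 6/19), two-sided 0.05 | 99.9% | 90.2% | Yes, but 0.972 is not used |
| AUC 0.89 against 0.5, equal groups, two-sided 0.01 | 100% | about 90% | Yes, but 0.972 is not used |

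The tests against 0.5 use power = Φ((0.39 − z·SE at 0.5)/SE at 0.89).

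**3. Margin implied by the stated power.** A margin of 0.082 gives Φ(−1.96) = 2.5% at any sample size, and a smaller margin gives less. For 99% at N=50 the margin is 0.082 + SE×(1.96 + 2.326) = 0.312, 0.260 or 0.219 for r = 0, 0.5, 0.8. For 91% at N=25 it is 0.082 + SE×(1.96 + 1.341) = 0.337, 0.279 or 0.234. A margin of 0.28 would accept an AUC of 0.972 − 0.28 = 0.69.

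**4. Precision of the AUC that 5.2 does estimate.** Simulation: equal-variance binormal data, true AUC 0.89, 20,000 runs per split, DeLong variance. Runs with an observed AUC of 1 (under 0.4%) are left out of the logit columns. The splits, and 40 analysed, are assumptions.

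| Cases/controls | Coverage of untransformed 95% interval | Upper limit above 1 | Mean lower limit, untransformed | Mean lower limit, logit scale | 10th–90th percentile, logit lower limit |
|---|---|---|---|---|---|
| 25/25 | 91% | 19% | 0.80 | 0.77 | 0.68–0.85 |
| 13/37 | 88% | 39% | 0.79 | 0.74–0.75 | 0.64–0.85 |
| 20/20 | 89% | 41% | 0.79 | 0.74 | 0.65–0.84 |
| 10/30 | 86% | 62% | 0.78 | 0.72 | 0.59–0.85 |

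The logit-scale interval covered about 95% in all four cases. The untransformed interval is too optimistic at these sizes to carry the sample-size argument.

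**The case against.** The strongest reply is that the design could support the comparison even though 5.2 does not make it. Section 3.1 enrols two clinically defined groups, subjects without chronic liver disease (low FIB-4) and subjects with known advanced fibrosis or cirrhosis, and 5.2 mentions baseline differences in each group. Both methods could be scored against that grouping. This stands as a limit on the point: what fails is the written analysis. A reader might infer that non-inferiority could never be examined in these subjects; the documents do not support that. But 5.2 does not use the grouping as its reference, and selecting on low FIB-4 or known cirrhosis would bring spectrum bias.

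A reader might also infer that 99% and 91% are miscalculated. They are not shown to be. Several different tests fit both figures, each with inputs the plan does not state, and the source of the pooled AUC lies in text that was not supplied. The most that can be said is that the supplied text does not tie the figures to the stated hypothesis.

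It could be argued that the AUC from 5.2 can simply be set against 0.972. That does not rescue the test: a value of 0.972 for MRE must rest on a reference other than MRE, so the two AUCs would not measure the same thing.

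Finally, the hypothesis may be loose wording, since 2.1 asks only for diagnostic performance compared with MRE. It is right that 5.2 can answer 2.1, so it would be too strong to say that the study cannot meet its primary objective. But the loose wording is the only hypothesis and the stated basis for N=50.

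**Conclusion.** The point holds and should be corrected before analysis. The contradiction between 5.1 and 5.2 rests on the text alone and needs no assumption: the planned analysis yields no contrast between EUS-SWE and MRE.

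The sizing is undocumented for the stated hypothesis. Under the assumptions above, a paired non-inferiority test at the cited AUCs has at most 2.5% power for margins up to 0.082 and 5–8% at N=50 for 0.10; it reaches 99% only with a margin of 0.22–0.31. These figures depend on the Hanley-McNeil variance, equal groups, correlation 0 to 0.8 and one-sided 0.025. They show how much the missing inputs matter, not that the sponsor's calculation was wrong.

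The defect is confined to the hypothesis and the sample-size statement. Data collection and the objective in 2.1 are unaffected.

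**What to change.** 1. In 5.1, replace the non-inferiority hypothesis with estimation: the primary measure is the AUC of EUS-SWE against the MRE-defined condition (definition to be set by the sponsor), with a 95% confidence interval on the logit scale using the DeLong variance, or by bootstrap.

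2. In 5.1, delete the 99%/91% statement and give expected precision. If the true AUC is 0.89, the mean lower logit-scale 95% limit is about 0.77 (25/25) or 0.74–0.75 (13/37) with 50 analysed, and about 0.74 (20/20) or 0.72 (10/30) with 40 analysed; the 10th–90th percentile range across these cases is about 0.59–0.85. Label the splits and the 40 as assumptions. Also reconcile whether the 50 are counted before or after unreliable SWE is removed: 4.2 lists it as exclusion 3, whereas 4.4.1 treats it as a withdrawal ("Then subjects will be withdrawn from the study and therefore will not proceed to undergo MRE, or to be included in the final analysis").

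3. In 5.2, state that no non-inferiority or equivalence claim against MRE will be made. Descriptive mention of the pooled 0.972 is acceptable.

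Only if the sponsor wants to keep non-inferiority: score both methods against one reference independent of MRE, state margin and alpha, compare the paired AUCs and redo the power. The clinical groups in 3.1 are the nearest option, with their spectrum bias acknowledged.

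Cost: the main fix is wording only, with no added subjects or procedures. The non-inferiority wording and the 99% figure are given up, and N=50 then rests on precision. Keeping non-inferiority needs a new analysis and, at a margin such as 0.10, probably far more subjects.

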1.1 Background

Shear wave elastography (SWE) uses shear waves to assess tissue elasticity in a non-invasive fashion. This technology has been incorporated into conventional trans-abdominal ultrasonography to evaluate for liver stiffness, especially in patients with suspected chronic liver disease. Endoscopic assessment of the liver is routinely performed during endoscopic ultrasound (EUS). Recent software package enhancements have allowed for the option of shear wave measurement during EUS procedures. To date, there is little to no literature on the performance of EUS SWE and its applicability in the assessment of liver fibrosis in the clinical setting. Therefore, we wish to determine the applicability of EUS SWE and evaluate its diagnostic accuracy compared to magnetic resonance imaging elastography, which is widely utilized to determine the presence of advanced fibrosis/cirrhosis in current clinical practice.

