3.1 General Design

This is a prospective, paired study. Study subjects who are scheduled to undergo EUS at Mayo Clinic will be identified through Epic. Chart review will be performed including review of prior imaging, medical history, and laboratory results as available in Epic to determine study eligibility. Subjects without history of chronic liver disease (screened by low FIB-4 score) and those with known advanced fibrosis/cirrhosis will be eligible for the study. Eligible study subjects will then be contacted either before, or at the time of their endoscopy procedure to discuss study participation. All subjects will then receive standard clinical care based on the indication for the EUS procedure. During the EUS procedure, study subjects with undergo shear wave measurements obtained in a non-invasive manner as part of the endosonographic evaluation of the liver. 10 measurements (including shear wave velocity (Vs), elastic modulus (E)) will be obtained for point SWE (pSWE). Measurements will be obtained from both left and right lobes of liver unless technically infeasible to do so. Study subjects will then undergo a paired MR elastography (same day or at later date) after completion of EUS and only if consistent and reliable shear wave measurements were obtained (e.g., VsN > 70% (reliability index of each measurement expressed in percentages), IQR/M (interquartile range/ Median) is <15% for Vs and <30% for E). Enrolled study subjects who had undergone a previous MRE (within 6 months of enrollment) would be eligible for the study, without the need to undergo further research MRE. After completion of MR elastography, the subjects will then continue through their routine clinical care and will not be followed up by research staff. The expected duration of subject participation is anticipated to begin at the time of study enrollment and terminate after completion of MR elastography. There will be no additional follow up.

3.2

Figure 1: Study Design

[figure not shown]

Table 1: Schedule of Events (SOE)

	Baseline Screening & Enrollment Visit 1 Days -180 to 0	Accrual: Study Intervention Visit 2 Day 0	Follow up Visit 3 Days 0 to 60
Inclusion/Exclusion	X		
EUS and Shear wave Elastography		X	
MRE	X*		X*

**MRE only required to be conducted once. Patients undergoing MRE for clinical purposes within the study timeframe can be recruited using the clinically performed MRE result.*

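### Section 5.1's non-inferiority hypothesis fits neither the MRE-referenced analysis in 5.2 nor the subjects admitted in 3.1, 4.1 and 5.3, and the stated 99%/91% power does not belong to it

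*Combined protocol and SAP*

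**What the plan says.** **Hypothesis.** Section 5.1 states that "EUS-SWE is non-inferior to MRE at differentiating" two groups, "cirrhosis vs those without fibrosis". Its inputs are "Using the pooled AUC above for MRE of 0.972" and a preliminary EUS-SWE AUC of 0.89. It claims 99% power with 50 subjects and 91% with 25. It gives no significance level, margin, null AUC or split between classes.

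**Analysis.** Section 5.2 estimates the AUC of EUS-SWE by logistic regression and ROC curves, with MRE as the gold standard, and refers to groups without defining them. Section 5.3 includes everyone who completes both tests.

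**Population.** Section 3.1: "Subjects without history of chronic liver disease (screened by low FIB-4 score) and those with known advanced fibrosis/cirrhosis will be eligible for the study". Section 4.1, item 2, is worded more widely: "Subjects with history of chronic liver disease, advanced fibrosis, or cirrhosis". Item 3 adds people with no such history.

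**Contrast elsewhere.** The Study Summary objective speaks of "liver fibrosis staging in both normal subjects and subjects with advanced liver fibrosis/cirrhosis". Section 12 describes the pilot as separating normal stiffness from advanced fibrosis/cirrhosis. As background, Section 1.1 says MRE is used "to determine the presence of advanced fibrosis/cirrhosis in current clinical practice", and the lead-in to Section 4 says that patients with "chronic liver disease with associated advanced fibrosis/cirrhosis will be of particular interest to the study".

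**The concern.** Three parts of the plan do not fit together.

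1. **Hypothesis and reference standard.** A test cannot be compared for accuracy with the standard that defines the truth. If MRE sorts subjects into diseased and not diseased, MRE separates those classes perfectly, and 0.972 is not a quantity this study can observe.
2. **Contrast and population.** A subject with advanced fibrosis but no cirrhosis is eligible under 3.1 and analysed under 5.3, yet belongs to neither class in 5.1. On the broad reading of 4.1, so does a subject with chronic liver disease and lesser fibrosis.
3. **Class boundary.** MRE gives a stiffness measurement, whereas logistic regression and ROC curves need a two-class outcome. The visible text does not say which MRE value divides the classes.

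The primary result therefore depends on choices that could be made after the data are seen. The power statement does not tell a reader what 50 subjects can show.

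**Working it through.** **Can the plan's power be reproduced?** Not from the stated inputs, because the significance level, margin, null value and class split are all missing. I tested the readings below with assumed values.

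**Standard error.** Hanley-McNeil, with n1 cases and n0 non-cases:

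SE² = [A(1−A) + (n1−1)(R1−A²) + (n0−1)(R2−A²)] / (n1·n0), where R1 = A/(2−A) and R2 = 2A²/(1+A).

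At A = 0.89 (Section 5.1): R1 = 0.8018, R2 = 0.8382, A² = 0.7921.

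- N=50, split 25/25: (0.0979 + 24×0.0097 + 24×0.0461)/625 = 0.00230, SE 0.048.
- N=50, split 15/35: (0.0979 + 14×0.0097 + 34×0.0461)/525 = 0.00343, SE 0.059.
- N=25, at 50% and 30% cases (fractional counts): SE 0.069 and 0.084.

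**Margin needed for the stated power.** One-sided 2.5%, true AUC 0.89, fixed comparator C:

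margin = (C − 0.89) + (1.96 + z_power)×SE.

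The multiplier is 1.96 + 2.326 = 4.286 for 99% and 1.96 + 1.341 = 3.301 for 91%. The deficit C − 0.89 is 0.082 for C = 0.972 and 0.11 for C = 1.

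| Case share | Stated power | Margin, C = 0.972 | Margin, C = 1 |
|---|---|---|---|
| 50% | 99% at N=50 | 0.288 | 0.316 |
| 30% | 99% at N=50 | 0.333 | 0.361 |
| 50% | 91% at N=25 | 0.309 | 0.337 |
| 30% | 91% at N=25 | 0.359 | 0.387 |

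Subtracting each margin from its comparator gives the same floor for either comparator. EUS-SWE would be called non-inferior if its AUC were shown to exceed a value of about 0.61-0.68.

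**Power with a margin of 0.10 at N=50.** Power = Φ[(margin − deficit)/SE − 1.96].

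- C = 0.972: Φ(0.018/0.048 − 1.96) = 5.7% at 25/25; Φ(0.018/0.059 − 1.96) = 4.9% at 15/35.
- C = 1: Φ(−0.010/0.048 − 1.96) = 1.5% at 25/25; Φ(−0.010/0.059 − 1.96) = 1.7% at 15/35.

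**If a third standard defined the classes.** A head-to-head comparison would then be possible, although 5.2 names no such standard. With an equal split and an assumed correlation of 0-0.8 between the two AUCs, the margin needed is about 0.22-0.31 for 99% at 50 and 0.23-0.34 for 91% at 25. A margin of 0.10 gives 5-8% power at 50.

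**What comes close to the stated figures.** Take 0.89 against 0.50, two-sided 5%, an assumed 25% cases, and the null variance for the critical value.

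- N=50: (0.39 − 1.96×0.0952)/0.0635 = 3.20, power 99.9%.
- N=25: (0.39 − 1.96×0.1360)/0.0908 = 1.36, power 91.3%.

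This match is not unique. A null of 0.71, one-sided 10%, equal split and the alternative variance gives 99.3% and 90.9%.

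**Precision with 50 completers.** Half-width = 1.96×SE. At AUC 0.89 it is 0.094 (25/25) to 0.115 (15/35). At AUC 0.80 it is 0.124 to 0.147.

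**The case against.** **The pooled MRE figure may be a fixed external benchmark.** This is fair. A reader might infer that non-inferiority cannot be tested at all, and that goes too far: the EUS-SWE AUC can be tested against 0.972 less a margin. What is missing on this reading is the margin, and the margin needed for the stated power is still about 0.29-0.36.

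**Clinical history could define the groups.** Section 3.1 does speak of known disease. But 5.2 gives the reference role to MRE and names no other standard.

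**The definitions may lie in material not supplied.** Section 5.1 refers to a pooled AUC given above that is not in the text, and Figure 1 is not shown. The statement about the cut-off is therefore limited to the visible text.

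**Some of the supporting passages are soft.** The Summary names groups for staging and is not a formal contrast. Section 1.1 describes clinical use, and the Section 4 lead-in describes recruitment interest. Reading 4.1 as admitting every stage of liver disease is its broadest reading. The mismatch stands without it, because 3.1 alone admits advanced fibrosis without cirrhosis.

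**The sponsor may prefer its own contrast.** That is acceptable if the analysis population is restricted to match.

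**Conclusion.** The point holds: as written, hypothesis, reference standard, contrast and population do not agree. The stated power is not that of the stated hypothesis under any margin near 0.10. It would need 0.29-0.36 against a fixed 0.972, or 0.32-0.39 with MRE at 1. These figures assume a true AUC of 0.89, one-sided 2.5%, 30-50% cases and a normal approximation. The 0.11 deficit also assumes that 0.89 was measured against MRE, and the documents do not state the pilot's reference standard.

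Two further inferences are tempting but unsupported:

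- **That the sponsor computed power against chance.** The near match needs an assumed 25% cases, and other nulls fit as well.
- **That classing the in-between subjects lowers the AUC by a particular amount.** The documents do not say which contrast gave 0.89, which stages will enter or where the MRE boundary lies. No size for that change should be quoted.

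**What to change.** 1. Reconcile 3.1 and 4.1 into one population statement.
2. Use one primary contrast in 5.1, 5.2 and 5.3, with the MRE cut-off fixed before analysis. Either of two choices works:
   - advanced fibrosis/cirrhosis versus not, for all completers, in line with the Summary and pilot, with cirrhosis versus no fibrosis as a labelled secondary contrast; or
   - 5.1's contrast, with the primary analysis in 5.3 restricted to those two classes and both of their MRE limits stated.
3. Restate the hypothesis as the AUC of EUS-SWE against MRE with a 95% CI, or against a stated null value. Replace 99%/91% with the matching precision or power, giving the significance level, null or margin, and class split.

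**Cost.** Wording in 3.1, 4.1, 5.1, 5.2 and, for the second choice, 5.3, plus the cut-off. It needs no extra tests, and the target of 50 need not change. The stated figures and the headline AUC may be less favourable. The second choice also loses subjects: if only 25 of 50 remained (an assumption, split 12/13), the half-width at AUC 0.89 would be 1.96×0.0697 = 0.137 instead of 0.094.
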